15.1.1.3. Planned dose of AGS-16C3F

Each subject's initial planned dose (mg) will be calculated as the prescribed dose level (mg/kg) times the baseline body weight (kg). If the subject's weight changes from baseline by $\pm 10\%$ or more during the study, then the new body weight will become the new "baseline" for recalculation of the dose at that visit and for any subsequent calculations of a $\pm 10\%$ change in weight. If the "baseline" body weight or the prescribed dose level changes at any time during treatment, then the planned dose will be recalculated.

15.1.1.4. Amount Taken in Milligrams (AGS-16C3F)

Amount of exposure to study drug will be reported as number of doses (infusions) started and total amount of drug used (mg) per subject. One dose per Cycle is planned.

The need for dose adjustment is collected on the eCRF and will not be imputed if missing.

15.1.1.5. Definition and Calculation of Treatment Delay

The protocol-specified dosing schedule is one dose every 21 days. If for logistical reasons (e.g., public holidays, clinic scheduling, etc.) the next dose cannot be given 21 days from the last dose, a -2 day and a +7 day dosing window is allowed.

Therefore, a delay is defined to have occurred when a subject has >28 days:

- Between 2 consecutive doses, or
- Between the date of the last dose administered and the earlier of (the date of the decision to stop treatment or the data cut-off date).

When a treatment delay occurs, it will be attributed to the later of the two doses. The length of the delay will be calculated as the difference between the two dates, minus the planned cycle time.

For example, suppose that the dates of the Cycle 4 and Cycle 5 doses were 35 days apart. The delay which occurred between Cycle 4 and Cycle 5 would be identified as belonging to Cycle 5 in the analysis dataset. The length of the

delay would be calculated as the date of the Cycle 5 dose minus the date of the Cycle 4 dose minus 28 days; given that the two doses were 35 days apart, this means the length of the delay would be 7 days.

15.2. AXITINIB

Descriptive statistics for the following study drug parameters will be presented for subjects who receive axitinib.

- Duration of treatment per subject, in weeks
- Total amount of medication used per subject, in milligrams
- A flag which indicates that a subject's initial prescribed Axitinib dose of 5 mg was increased at any time during the treatment period.
- A flag which indicates that a subject's initial prescribed Axitinib dose of 5 mg was decreased at any time during treatment.

15.2.1. DERIVATIONS RELATED TO AXITINIB EXPOSURE

15.2.1.1. Dates of First Dose and Last Dose of Axitinib

For subjects who receive axitinib, the date of first dose of axitinib will be the earliest dosing date recorded on the Axitinib Drug Administration eCRF.

The date of last dose will be taken from the "Subject Status – Completion" form. For any subject for whom a last dose date is unavailable at the time of database lock or data cut-off, a last dose date will be imputed as the earliest of:

- The date of discontinuation from study
- The date on which the last dose from the last bottle could have been taken, if the medication had been taken as prescribed; if the imputation of last dose date is based on the last bottle dispensed, then the earlier of the bottle return date or a date based on the total number of doses in the bottle will be used
- The subject's death date
- The day prior to the first dose of any non-study cancer regimen

For subjects who are still on treatment at the time of any interim reporting event, including all IDMC data review meetings and the Main Analysis, the date of last dose may be imputed as the data cut-off date for calculations that require a date of last dose.

15.2.1.2. Duration of Treatment with Axitinib

For subjects who are on treatment, the duration of treatment (days) will be calculated as the data cut-off date minus date of the first dose + 1. For subjects who have gone off treatment, the duration of treatment (days) will be calculated as the last dose date minus the date of the first dose + 1. In each case, the calculation will be made without consideration of interruptions, compliance, or dose changes. Treatment delay time will be included, unless the subject discontinues from the study without resuming treatment.

If the subject discontinues from study, is lost to follow-up, or dies, and the last dose date remains unavailable at the time of database lock or data cut-off, then the imputed date of last dose will be used in calculating the duration of treatment. Duration of treatment in days will be converted to duration of treatment in weeks, rounded to the closest 1/10) for summary tables and listings, using the following formula:

Number of weeks = round ((number of days/7), 0.1).

15.2.1.3. Planned Amount in Milligrams (Axitinib)

Axitinib comes in two strengths (5mg and 1mg tablets) and each subject can be prescribed an axitinib dose ranging from 2 mg to 10 mg per dose, to be taken twice daily. The prescribed amount (mg) per dose is collected in the Axitinib Administration eCRF.

During any dosing interval, the planned amount of axitinib (mg) can be calculated as the prescribed amount (mg) per dose x 2 doses per day x the number of days in the dosing interval. The overall amount (mg) of axitinib planned to be taken by a subject can be calculated by summing the number of planned milligrams across all dosing intervals for the subject.

15.2.1.4. Amount Taken in Milligrams (Axitinib)

In any dosing interval, the amount (mg) taken will be calculated as (the number of 1mg tablets dispensed at the previous visit minus the number of 1mg tablets returned at the current visit) plus 5 x (the number of 5mg tablets dispensed at the previous visit minus the number of 5mg tablets returned at the current visit). The total amount taken (mg) during the study will be calculated by summing the amounts taken by a subject in all dosing intervals.

It will be assumed that pills not returned during the course of the study were taken by the subject as planned, up to and including the date of actual or imputed last dose. It will be assumed that no study drug was taken after the imputed date of last dose.

If a subject fails to return a bottle on schedule, but returns it within 7 days of the planned time, the return will be treated as an on-schedule return for data handling purposes. If a bottle is returned more than 7 days late, then it will be assumed that the subject took the drug on a consistent, personal schedule; and therefore the amounts returned and taken will be averaged over the two affected time intervals.

15.2.1.5. Subject Exposure to Axitinib

Amount of exposure to study drug will be reported as amount of drug used (mg).

15.2.1.6. Determination of Dosing Intervals (Axitinib)

Dosing intervals must be defined to support accurate calculation of the amount of drug planned or taken. In general, a dosing interval will start at a visit when study drug is dispensed and end at the next consecutive visit when study drug is returned. The following data-driven cases may also apply:

- If the prescribed dose changes between visits, the date of the prescription change will signal the end of one dosing interval and start of another.
- If study drug is dispensed or returned at an unscheduled visit, that visit will signal the end of one interval and start of the next.

Other rules for handling special cases may be developed during programming and will be documented in the analysis dataset specifications.

16. COMPLIANCE

16.1. COMPLIANCE WITH STUDY DRUG

Descriptive statistics for overall percent compliance by subject will be presented for the axitinib group in the SAF.

16.1.1. DERIVATIONS RELATED TO STUDY DRUG COMPLIANCE

Compliance will be measured using the overall percentage of planned exposure for each subject. Percent of planned exposure will be calculated as $100 \times \text{amount taken (mg)} / \text{amount planned (mg)}$. Section 15.2.1 presents the derivations of the planned amount (mg) and amount taken (mg).

16.2. COMPLIANCE WITH DISEASE ASSESSMENT SCHEDULE

A disease assessment is considered compliant with the disease assessment schedule if it is performed within the protocol-specified window. A disease assessment that is performed outside the protocol-specified window, or not performed, is considered to be noncompliant with the protocol-specified schedule.

A descriptive analysis of compliance to the disease assessment schedule will be provided by treatment arm. The number and percentage of off-schedule disease assessments will be calculated and listed for each subject. A table showing the number of subjects with 1 or more off-schedule disease assessments, the total number of off-schedule disease assessments during the study, and descriptive statistics for the number and percentage of off-schedule disease assessments per subject, by treatment arm, will be produced.

16.2.1. DERIVATIONS RELATED TO COMPLIANCE WITH DISEASE ASSESSMENT SCHEDULE

For each subject, the planned disease assessment schedule will be compared to the subject's actual disease assessment schedule. A planned disease assessment will be considered off-schedule if no disease assessment was performed within the planned, protocol-specified assessment window. Missing disease assessments will be included in the counts of off-schedule assessments.

17. EFFICACY

Efficacy analyses will be conducted on the FAS and PPS. The FAS will be considered as primary and the PPS will be used as secondary to assess "sensitivity to analysis sets", i.e., the robustness of the results from the statistical analyses based on the FAS.

17.1. PRIMARY EFFICACY

17.1.1. PRIMARY EFFICACY VARIABLE & DERIVATION

The primary efficacy endpoint is progression-free survival (PFS), which is defined as the time from the date of randomization to the earliest of documented disease progression (as defined by RECIST v 1.1 per investigator

radiology review) or death from any cause. Disease assessment will continue until disease progression, even after the originally assigned treatment is discontinued. Subjects for whom progression or death do not occur will be censored according to rules described in Section 17.1.2.

The primary efficacy variable is comprised of PFS times which are calculated after applying the censoring rules that were specified for each analysis. PFS time will be calculated (in months) as (the earliest date of progression, death, or censoring, minus the randomization date, plus 1) divided by 365.25 days per year, times 12 months per year. PFS in tables and listings will be displayed to the closest 1/10 of a month.

17.1.2. MISSING DATA METHODS FOR PRIMARY EFFICACY VARIABLE

The analyses of PFS in this study are designed to be consistent with FDA guidance documents and the EMA scientific guidelines for analysis of PFS.

The EMA Guideline on the Evaluation of Anticancer Medicinal Products in Man (CHMP/EWP/205/95 Rev 34), Appendix 1, suggests that the primary analysis of PFS (defined as death or documented disease progression) should follow the ITT principles and be based on actual death dates and actual date of documentation of disease progression.

PFS Censoring Rules (Set 1) are designed to match this guidance except that subjects who receive non-protocol anticancer treatment without death or documentation of disease progression beforehand will be censored at the date of last disease assessment prior to the start of non-protocol anticancer treatment per May 2007 FDA Guidance for Industry “Clinical Trial Endpoints for the Approval of Cancer Drugs and Biologics”.

The guidelines also suggest that sensitivity analyses should be conducted to address important assumptions in the methods used, including the handling of deviations and missing data, censoring for subsequent anti-cancer treatment, non-radiological disease progression, and the handling of unscheduled evaluations. The PFS Censoring Rules (Sets 2, 3, 4) described in the sections below are designed to produce sensitivity analyses which address some of these concerns.

Under each set of censoring rules, if a subject fulfils the criteria for more than one situation, then the most conservative applicable outcome (“progressed”, followed by “censored”) will be assigned to the subject. Also, the shortest applicable time to event within the assigned outcome category will be used for the analysis.

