17.1.2.1. PFS Censoring Rules (Set 1)

The PFS Censoring Rules (Set 1) will be used to manage missing data in the primary analysis of PFS. Under the Set 1 rules, PFS will be right-censored for subjects who meet one or more of the following conditions:

- Subjects with no post-baseline disease assessments (unless death occurred prior to the first scheduled assessment, in which case death will be considered a PFS event)
- Subjects who initiate subsequent anticancer therapy or intervention in the absence of documented progression
- Subjects who die or have disease progression after missing 2 or more consecutively scheduled disease assessment visits
- Subjects who are last known to be alive and progression-free on or before the data cut-off date

For such subjects, PFS will be right-censored according to the conventions described in Table E. These conventions are based on the May 2007 FDA Guidance for Industry “Clinical Trial Endpoints for the Approval of Cancer Drugs and Biologics”.

Table E. PFS Censoring Rules (Set 1): Date of Progression or Censoring

Situation	Date of Progression or Censoring	Outcome
Death before first scheduled disease assessment	Actual date of death	Progressed
Documented disease progression before first scheduled disease assessment	Actual date of disease assessment at which progression was noted	Progressed
Death or documented disease progression between 2 scheduled disease assessments	Actual date of death or actual date of first disease assessment showing documented disease progression, whichever occurs first	Progressed
Missed ≥ 2 consecutive disease assessments immediately prior to death or progression	Actual date of last non-missing disease assessment that is before the missed visits and prior to death and prior to documented disease progression	Censored
No death and no post-baseline disease assessments	Actual date of randomization	Censored
Non-protocol anticancer treatment started prior to death or prior to documentation of disease progression	Actual date of last non-missing disease assessment prior to start of non-protocol anticancer treatment	Censored
Alive and not progressed [1]	Actual date of last non-missing disease assessment	Censored

[1] Without death and without documentation of disease progression; includes subjects who may have discontinued from study prior to death and without documentation of disease progression.

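### The progressed-before-censored ranking in SAP 17.1.2 conflicts with the Set 1 row that censors primary PFS when new anticancer therapy starts before the event

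*SAP*

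**What the plan says.** **The ranking.** SAP 17.1.2 applies one tie-break to all rule sets: "if a subject fulfils the criteria for more than one situation, then the most conservative applicable outcome (“progressed”, followed by “censored”) will be assigned". It adds that "the shortest applicable time to event within the assigned outcome category will be used for the analysis". Set 1, the primary set, is not exempted.

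**The censoring rules it meets.**
- SAP 17.1.2, describing Set 1: "subjects who receive non-protocol anticancer treatment without death or documentation of disease progression beforehand will be censored at the date of last disease assessment". The sentence gives this as the one exception to using actual death and progression dates.
- SAP 17.1.2.1: "PFS will be right-censored for subjects who meet one or more of the following conditions". The list includes starting subsequent anticancer therapy without documented progression, and dying or progressing after two or more missed visits.
- SAP Table E: "Non-protocol anticancer treatment started prior to death or prior to documentation of disease progression" has outcome Censored, at the last assessment before that therapy. Another row censors when two or more assessments were missed immediately before the event.
- Protocol 7.4.1.1 and Table 13 (version 6.0) censor both situations and contain no such ranking.
- SAP 17.1.2.2 describes Set 2 as widening the Set 1 event definition to take in both groups, so Set 1 should not already count them.

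**The event rows.** Table E assigns Progressed for "Death before first scheduled disease assessment", for documented progression before that assessment, and for "Death or documented disease progression between 2 scheduled disease assessments". None excludes a subject who has already started new therapy.

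**Time.** SAP 17.1.1 computes PFS time from "the earliest date of progression, death, or censoring, minus the randomization date, plus 1", after the censoring rules have been applied.

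**The concern.** A subject who starts new therapy and then dies can fit both an event row and a censoring row. The general sentence in 17.1.2 makes that subject an event at the date of death. The specific row makes the same subject censored at the last scan before the switch. Two programmers, each following the SAP, can therefore produce different primary data.

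Set 1 status and time feed the primary stratified log-rank test (SAP 17.1.3), and the Set 1 event count fixes the Main Analysis cut-off (SAP 4.2). The trial is open-label, so switching before progression may differ by arm. Calling an event the conservative outcome is then not assured in a two-arm superiority test, because the direction depends on which arm holds more of these subjects.

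**Working it through.** **1. The plan's own figure.** Events = 4(z0.90 + z0.80)² / (ln 0.667)² = 4(1.2816 + 0.8416)² / 0.1640 = 109.95, or 110. Critical hazard ratio = exp(−2 × 1.2816/√110) = 0.783. Both reproduce, and neither depends on this point. For the cut-off, suppose that 110 counted events included k subjects whom the test then censored. Power is Φ(√(110−k) × ln 1.5/2 − 1.2816), which is 80.1% for k = 0, 78.7% for k = 5 and 77.2% for k = 10.

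**2. Which Table E rows can collide.** The rows for no death and no post-baseline scan, and for alive without progression, cannot coincide with an event row. The new-therapy and missed-scan rows can, so these are the only Set 1 rows on which the ranking can act.

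| Subject | Event row | Censoring row | Overlap |
|---|---|---|---|
| New therapy, then death or progression before first scheduled scan | Fits | New therapy | Certain |
| New therapy, then death later | Fits if the between-assessments row means planned dates | New therapy | Depends on reading |
| Two or more missed scans, then death or progression | As above | Missed scans | Depends on reading; planned dates would largely empty this row |
| New therapy, no recorded death or progression | None | New therapy | None |

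Table E does not settle the reading. Unlike Table G, it has no row for progression at a scheduled assessment. Sets 3 and 4 carry the same conflict. In Set 2 both situations are already events, so nothing is overridden.

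**3. Size.** The documents give no switching rate, so this is simulation on assumptions.
- From the documents: 134 subjects, 1:1, 7 per month, control median 4 months, scans every 8 weeks, 10% lost, one-sided 0.1, month 24.
- Assumed: 5%, 10% or 20% switch before documented progression, with exponential survival after switching (median 6, 12 or 18 months).
- Readings: A censors at the last scan before the switch. B counts the later death as an event at its date (planned-calendar reading).
- There were 5,000 runs per scenario. The standard error at 0.10 is √(0.1 × 0.9/5000) = 0.004.

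| Quantity | Switching | A | B |
|---|---|---|---|
| Estimated HR, true HR 0.667 | Equal | 0.699-0.700 | 0.701-0.706 |
| Rejection, true HR 1 | Equal | 0.099-0.103 | 0.099-0.104 |
| Rejection, true HR 1 | 5% v 20%, both directions | 0.099-0.102 | 0.070-0.145 |

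At a true HR of 0.667 with equal switching, deaths before the first scheduled scan average 0.06-0.85 subjects. Reading B changes 1.7-3.5 subjects at 5% switching, 3.5-7.2 at 10% and 7.5-15.1 at 20%. A and B reach opposite decisions in 2.3-9.2% of trials. A simpler model (4,000 runs, no scan grid, 8-month median after switching) adds 3.2, 6.5 and 13.6 events and gives opposite decisions in 2.8%, 4.7% and 8.1%.

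**4. Limits of the simulation.** The log-rank test is unstratified. Missed scans are not modelled. The month-24 cut yields about 88-93 events under A at 5-10% switching and HR 0.667, not 110. An event-driven rerun at HR 1 gave rejection of 0.108 v 0.109 (A v B) with equal 10% switching, and about 0.07-0.16 with a four-fold imbalance.

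**5. A missing date.** If new therapy starts before any post-baseline scan, the last assessment is the screening scan. Screening is completed before randomization (Protocol 5.2.5). By the 17.1.1 formula, a scan one day before randomization gives −1 + 1 = 0 days, and an earlier scan gives a negative time.

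**The case against.** **Intent is clear for new therapy.** One general sentence stands against several specific ones, including one in the same section, and a sensible programmer would follow the row. This is a fair reason to grade the point below a must-fix. It does not remove the conflict: no sentence says that the specific row governs, and the ranking was written to resolve overlaps.

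**The certain overlap is tiny, and the rest is conditional.** This stands. Scheduled scans stop when a new therapy starts (SAP 3.1, Protocol 5.5), so the wider new-therapy overlap is essentially deaths. A milder assumed imbalance of 8% v 12% (1,500 runs, 12-month median after switching) gave rejection at HR 1 of 0.099 v 0.101 in one direction and 0.116 v 0.117 in the other, with no visible shift between readings. Opposite decisions in 2-9% of trials reflect borderline results and are not evidence of bias.

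**Missed scans are less one-sided.** This also stands. SAP 17.1.2 names new therapy as the only exception to actual event dates, which supports counting events after missed scans. Table E, the Set 1 bullets, Protocol Table 13 and the Set 2 text point the other way.

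**Stronger inferences that the documents do not support.** A reader might infer from the earliest-date wording in 17.1.1 that event status would be paired with the earlier censoring date. But 17.1.1 calculates time after the censoring rules are applied, and 17.1.2 takes the shortest time within the assigned outcome. A reader might also infer that the SAP departs from its governing protocol. The SAP cites version 4.0, which is not available here; only version 6.0 can be compared.

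**Conclusion.** The conflict is real and sits in the primary endpoint definition: a stated rule can assign an event where the plan elsewhere prescribes censoring. It is certain for new therapy followed by death or progression before the first scheduled scan. For later deaths and for missed scans it depends on an ambiguous Table E row.

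The size and direction of the effect cannot be known from the documents. On the assumed inputs, the certain overlap is under one subject on average for deaths at HR 0.667. On the wider reading, equal switching leaves the hazard ratio and type I error almost unchanged. Rejection at HR 1 reaches about 0.07-0.15 only under an assumed four-fold imbalance. It would be tempting to conclude that the primary result is biased, but nothing in the documents supports that. Should fix, before lock.

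**What to change.** In SAP 17.1.2:
- State that in Sets 1, 3 and 4 the new-therapy censoring row takes precedence over any later event row.
- State that the missed-scan row does too, as in Table E and Protocol Table 13, and amend the exception sentence to name it. If these events are meant to count, change Table E instead and log it in Table A.
- Limit the progressed-first ranking to other overlaps and to Set 2.

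In 17.1.1, state that PFS time runs to the date given by the assigned row. In Table E, give a censoring date for new therapy started before any post-baseline scan; randomization is one option.

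Reconcile Set 1 bullet 1 with Table E for a subject with no post-baseline scan who dies after the first scheduled assessment. The bullet censors, whereas Table E restricts its no-scan row to subjects who have not died.

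The cost is a few sentences of SAP text before lock. No new data are needed and no sample-size figure changes.
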